Effects of trans-cutaneous spinal direct current stimulation in incomplete spinal cord injury

NCT03249454

Version Date: 08/18/2017

UNIVERSITY OF TEXAS – HOUSTON MEDICAL SCHOOL PROTOCOL

PROTOCOL TITLE: Effects of trans-cutaneous spinal direct current stimulation in incomplete spinal cord injury

2. BACKGROUND and SIGNIFICANCE

According to the National Spinal Cord Injury Statistical Center, as many as 300,000 people in the United States are living with spinal cord injury (SCI), with approximately 17,000 new cases each year.¹ Unfortunately, efforts to minimize neurologic damage in acute SCI have met with only limited success.^{2,3} Complete recovery is reported in less than 1% of SCI survivors.¹ Thus, there is a need for interventions to enhance recovery of function for people living with chronic effects of SCI. Recovery of motor function after chronic SCI has been associated with neuroplastic changes.^{4,5}

Transcranial direct current stimulation has been shown to significantly influence corticomotor excitability (a marker of neuroplasticity).⁶⁻⁹ The polarity of the current is important in direct current stimulation: anodal stimulation over the primary motor cortex leads to a depolarization of the neuronal membrane's resting potential and thus increases motor cortical excitability; cathodal stimulation causes the opposite effect.¹⁰⁻¹² Early human and animal studies suggest similar modulation of spinal cord excitability after transcutaneous spinal direct current stimulation (tsDCS). Possible mechanisms include alteration of GABAergic and glutamatergic systems.¹³⁻²² However, data in this regard is very limited and inconsistent.^{18, 19, 22, 23} This study addresses this gap in research by conducting a exploratory project that will evaluate the effects of tsDCS on spinal excitability. This pilot study will provide preliminary support and effect sizes that will be used in a larger federally funded study. Many symptoms and signs of SCI, such as hyperreflexia and spasticity are associated with H-reflex alteration.²⁴ Therefore, demonstrating changes in the amplitude of H reflexes might be of potential clinical importance since these changes have been related to the acquisition of new motor skills and in restoration of motor functions in both animals and humans.²⁵⁻²⁹ The H-reflex is used commonly to study the excitability of spinal motor circuitry as a surrogate for functional adaptation and neuroplastic changes that may occur in relation to injury, disease, or therapeutic interventions.^{26, 30-32} Thus, given the previous finding that tsDCS can alter H reflex²² we hypothesize that tsDCS is capable of inducing plastic changes of excitability in the monosynaptic pathway mediating the H-reflex, when tested using stimulation rates at which post-activation depression is present.

SSEPs after stimulation of posterior tibial nerve are absent in complete lesions of the spinal cord. However, incomplete lesions yield varying abnormalities on SSEPs. Latencies and amplitudes of tibial SSEPs can change over time after spinal cord injury (SCI). SSEPs have been studied as a surrogate measure to evaluate for neuroplasticity after cortical and spinal

cord stimulation.^{17, 33, 34} However, there are no robust studies that evaluated effects of tsDCS on SSEPs.

In sum, and in contrast to most other studies of tsDCS, our design expedites early-stage investigation of this promising intervention by establishing strong, electrophysiological data prior to rapid clinical translation of findings. In general, our proposal has exceedingly high translational potential. The non-invasive stimulation we propose (tsDCS) is delivered by a portable device that can be easily carried and applied in a diversity of clinical settings, including inpatient and outpatient rehabilitation.

3. PURPOSE OF THE STUDY:

The purpose of the study is to investigate the effects of a novel therapeutic approach to promote functional recovery and spasticity in chronic SCI. We will evaluate tsDCS effect on neurophysiological measure such as H reflex and SSEP in subjects with SCI. This incremental, design will allow us to establish strong, electrophysiological data prior to rapid clinical translation of our findings about this promising, early-stage technique.

The central hypothesis is twofold: 1) active tsDCS will lead to a change in Hmax/M max ratio than sham tsDCS, in a polarity dependent manner; and 2) active tsDCS will lead to a change in SSEP amplitude and latency, in a polarity dependent manner.

Hypothesis: To evaluate the effects of tsDCS and different polarities on spinal excitability as measured by change in Hmax/M max ratio and SSEPs.

Hypothesis 1: In subjects with motor incomplete SCI, either anodal or cathodal tsDCS placed at the T10-T11 level will result in a change in spinal excitability evident by change in Hmax/M max ratio.

Hypothesis 2: In subjects with motor incomplete SCI, either anodal or cathodal tsDCS placed at the T10-T11 level will result in a change in spinal excitability evident by change in somatosensory evoked potential (SSEP).

4. DESCRIPTION OF STUDY:

Subjects will be screened in the outpatient SCI clinic. Each subject will receive five tsDCS (2 cathodal, 2 anodal and 1 sham) conditions at T10-T11 spinal level in a random order. There will be a wash-out period of 1 week between each tsDCS condition. Saline soaked sponge electrodes (36 cm²) will be used to deliver active tsDCS over skin at specified level. Reference electrode will be placed over left shoulder. Active tsDCS (i.e., anodal or cathodal; not sham) will consist of stimulation at an intensity of 2.5 mA for the entirety of each stimulation session (i.e., 2.5mA for 15 minutes to result in a current density of 0.071mA/cm² and a total delivered charge of 0.064C/cm²). This current density was proven to be safe and sufficient to induce

physiological changes in previous human studies.^{17, 19, 35} In a study done on healthy subjects ([name] PI), current densities above this range resulted in skin blisters. For sham tsDCS, we will start at 0mA and ramp the intensity up, then down, over a 30-second window. This protocol has proven effectiveness for blinding subjects in studies applying direct current stimulation.

Pre-screening: During the pre-screening process, potential subjects with incomplete SCI will be contacted by phone or in person by [name] (PI) or other co-investigators. [name] will give final approval for the subject to come to The Institute for Rehabilitation and Research Memorial Hermann for the screening procedure.

Screening (Visit 1, duration: One hour): This visit will occur the same day as intervention visit. After subject arrives at TIRR a research personnel will meet him/her at the Motor Recovery Laboratory. The details of the study- specific procedures will be reviewed with the subject together. Subject will be screened for inclusion and exclusion criteria. Signed and dated informed consent will be obtained. Demographics, medical history, list of medications and modified ashworth scale score will be recorded. If the subject is female in child bearing ages, a urine pregnancy test results from primary care physician will be requested. A medication diary will be given to the subject and asked to document all changes in type and dosage of the medication he/she has been using throughout the study. This will allow us to differentiate a potential effect of a change in dosage or type of medication on movement recovery. After subject meets all Inclusion and Exclusion Criteria the randomization will be done by means of sealed, opaque, consecutively numbered envelopes constructed by the research assistant. Each envelope will have intervention sequence information. Sequence will be generated by a random number generator. The research assistant will assign 1 envelope to each subject randomly. Each envelope will be opened by the research assistant prior to first session who will administer tsDCS. The research assistant will not be involved in data analysis or measurement of outcomes.

Intervention (duration: three hours): This visit is divided in to baseline, tsDCS stimulation and post tsDCS.

Figure1 : Intervention Visit: Baseline H_{max}/M_{max} and SSEP will be performed before actual tsDCS intervention. Post

intervention Hmax/Mmax and SSEP will be performed after the tsDCS

Baseline: The baseline assessment will be performed on the same visit as intervention and will be performed in the Motor Recovery Laboratory by an evaluator blinded to subject's group assignment.

Vital Signs: Vital signs will be recorded at the beginning of each session.

SSEPs: We will measure SSEPs to evaluate effects of tsDCS on ascending somatosensory pathways. A somatosensory evoked potential (SSEP) is the electrical activity response measured at the skin's surface along ascending sensory pathway following controlled peripheral nerve stimulation. For recording posterior tibial nerve SSEPs, the nerve is stimulated at the ankle, with the cathode midway between the Achilles tendon and the medial malleolus and the anode 3 cm distal to the cathode. Nerve stimulation should consist of a 0.1–0.2 ms duration square wave pulse at 3–5Hz. These pulses will be delivered by constant voltage stimulator applied transcutaneously over the targeted nerve. The stimulation intensity would exceed the motor threshold for eliciting a muscle twitch.³⁷ We will use same Nihon Kohden clinical EMG/NCV measuring system to measure SSEPs. Procedure will follow per clinical protocol.

Hmax/Mmax ratio: Immediately before and after application of tsDCS we will measure Hmax/Mmax ratio obtained from soleus muscle by stimulation of tibial nerve. The difference between pre and post Hmax/Mmax ratio will be measured. The H-reflex is a compound muscle action potential elicited by low-threshold electrical stimulation of afferent fibers in the mixed nerve with subsequent monosynaptic excitation of alpha motoneurons. Changes in the excitability of the reflex pathway are estimated by measuring the amplitude of the reflex. M wave is a compound muscle action potential produced by direct supra-maximal stimulation of motor axons. The H-reflex amplitude is highly variable, the excitability of the motoneuron pool plays a substantial role in determining the amplitude of the H-reflex. Therefore, changes in the ratio of maximal H-reflex amplitude and maximal M-wave amplitude (Hmax/Mmax) provide a rough estimate of modulation in spinal excitability.^{18, 19, 22} It is necessary to normalize this value so between-subject comparisons can be made. These amplitude variations can result from variations in skin resistance, different amounts of subcutaneous fat, and locations of the nerve relative to the stimulus, among others. The most advocated method of H-reflex normalization is eliciting the H-reflex at a percentage of the Mmax. This method entails finding the amplitude of the Mmax and then adjusting the stimulation intensity to produce an H-reflex with amplitude equal to some percentage of the Mmax amplitude.³⁶

[figure not shown]

Figure 2: M wave and H reflex

tsDCS Stimulation: Spinal stimulation direct current will be delivered by a battery-driven direct current stimulator (Soterix Medical, Model 0707-A) connected to a pair of saline-soaked sponge electrodes. Each subject will receive five tsDCS conditions at T10-T11 spinal level with a wash-out period of 1 week between 2 cathodal, 2 anodal and 1 sham tsDCS in a random order. Saline-soaked sponge electrodes (36 cm²) will be used to deliver active tsDCS over skin at specified level. Reference electrode will be placed over left shoulder. Active tsDCS (i.e., anodal or cathodal; not sham) will consist of stimulation at an intensity of 2.5 mA for the entirety of each stimulation session (i.e., 2.5mA for 15 minutes to result in a current density of 0.071mA/cm² and a total delivered charge of 0.064C/cm²). This current density was proven to be safe and sufficient to induce physiological changes in previous human studies.^{17, 19, 35} In a study done on healthy subjects ([name] PI), current densities above this range resulted in skin blisters. For sham tsDCS, we will start at 0mA and ramp the intensity up, then down, over a 30-second window. This protocol has proven effectiveness for blinding subjects in studies applying direct current stimulation. Figure 3 shows the study design.

Randomized cross over design
15 subjects with incomplete SCI will receive these interventions in random fashion (5 sessions per subject, total 75 sessions)
Cathodal tsDCS
Anodal tsDCS
Sham tsDCS
Cathodal tsDCS
Anodal tsDCS

Figure 3 Study Design:Randomization

Post tsDCS: Hmax/Mmax ratio, SSEP and vital signs will be recorded. Similar procedures will be followed as pre intervention assessments for Hmax/Mmax ratio, SSEP and vital signs recordings.

Adverse events: Any adverse events during intervention and collection of pre and post intervention outcomes assessments will be collected.

Assessment	Screening	Intervention 1 (Anodal or Cathodal or Sham)	Washo ut	Intervention 2 (Anodal or Cathodal or Sham)	Washou t	Intervention 3 (Anodal or Cathodal or Sham)	Washo ut	Intervention 4 (Anodal or Cathodal or Sham)	Washout	Intervention 5 (Anodal or Cathodal or Sham)
	0-30 days prior	Session1	atleast 8 days	Session 2	atleast 8 days	Session 3	atleast 8 days	Session4	atleast 8 days	Session5
ICF	X									
I/E Criteria	X									
Randomization	X									
Demographics	X									
Medical History	X									
Modified Ashworth Scale	X									
Baseline Vital Signs		X		X		X		X		X
Baseline SSEP		X		X		X		X		X
Baseline Hmax/Mmax		X		X		X		X		X
tsDCS		X		X		X		X		X
Post SSEP		X		X		X		X		X
Post Hmax/Mmax		X		X		X		X		X
Post Vital Signs		X		X		X		X		X
Questionnaire		X		X		X		X		X
Adverse Events		X		X		X		X		X

Table 1: Schedule of visits for SCI participant.

5. SUBJECT POPULATION:

Fifteen adults with SCI will be recruited from TIRR Memorial Hermann, TIRR Outpatient Rehabilitation at Kirby Glen and from the Houston area.

Inclusion Criteria:

1. Providing written informed consent prior to any study related procedures;
2. 18-65 years of age;
3. Motor incomplete SCI classified as B, C or D by the American Spinal Injury Association Impairment Scale (AIS);
4. Traumatic lesion at or above T8-T9 neurological level
5. Body mass index ≤ 30 (in order to facilitate reliable location of body landmarks guiding stimulation);
6. Chronic SCI (time since injury >6 months)

Exclusion Criteria: Subjects will be excluded if they have following conditions

1. Unstable cardiopulmonary conditions;
2. History of seizure, head injury with loss of consciousness, severe alcohol or drug abuse, and/or psychiatric illness;
3. Any joint contracture or severe spasticity, as measured by a Modified Ashworth Score 4;
4. Subject who cannot provide self-transportation to the study location;
5. Cardiac or neural pacemakers;
6. Pregnancy
7. h/o lower motor neuron injury (eg: peripheral neuropathy, cauda equina syndrome)
8. Uncontrolled diabetes with HbA1C >7 ;
9. History of severe autonomic dysreflexia;
10. alteration in therapy or medication for muscle tone during the course of the study (botulinum toxin injections in last 3 months, phenol injections in last 6 months, intrathecal baclofen pump dose stable for past 3 months, etc);
11. Conditions for e.g., severe arthritis, extreme shoulder pain that would interfere with valid administration of the measures or with interpreting motor testing;
12. contraindications to tsDCS:
- ferromagnetic material in the brain or in the spine (except for titanium used in segmental 9

fixation of the spine)

- implanted brain medical devices

6. SUBJECT ENROLLMENT:

Potential subjects will be identified by the following sources:

1- Flyers will be posted in the TIRR Memorial Hermann outpatient clinic, TIRR Memorial Herman Adult and Pediatric Outpatient Rehabilitation Kirby Glen, MHH Rehabilitation Centers. Attending physicians and therapists may refer their acquired brain injury outpatients to the study. In order to reach out to individuals with SCI; flyers will be distributed through an e-mail distribution.

2- After subjects are identified by their treating physicians and therapists, they will be referred to the co-investigator. During this first contact, the researcher will briefly explain the study content and request their phone number and e-mail address to contact them later for a pre-screening. During a phone call, a brief pre-screening procedure will be followed. Demographics and medical information such as surgery implants, medications, psychiatric, drug and alcohol history as inclusion and exclusion criteria will be gathered. [name] will review the information gathered during phone screening and may request screening.

3- Potential subjects will be invited to come for a screening visit to Motor Recovery Laboratory at TIRR Memorial Hermann. Any information gathered during phone screening will be stored in a locked file cabinet and password protected electronic file. During the screening visit, an investigator at TIRR will obtain informed consent. The test procedures will be described and the testing equipment will be shown to the subject. Investigator will clearly explain all the procedures and risks of the testing outlined in the consent form. The subject will be given sufficient time to consider their decision and will be encouraged to ask questions, both during the initial interview and throughout the study. The PI or a co-investigator will answer any questions regarding the study at the time consent is given. Once enrolled, the subject may pause or terminate his/her participation at any time during the study.

4- Alternatively any person with SCI who are living in the community and been informed through flyers can contact the researchers directly and request more information about the study.

7. DATA ANALYSIS:

Data analysis: Descriptive statistics will be calculated for all variables. Group analysis of intervention-related changes with fixed effects comparison of post-intervention versus baseline will be performed. We will use repeated measures analysis of covariance to estimate the effect

of group on outcome measures. Stata 14 software will be used to perform analysis. PI has training to use stata software to perform above analysis.

A sample size of 15 subjects was determined based on the review of current literature to determine the optimal polarity for future studies.^{17, 19, 22, 35} In these studies 10-12 healthy subjects were evaluated who received one anodal tsDCS, one cathodal tsDCS and sham (total 3 sessions) in cross over fashion. In our study, we plan to deliver 2 cathodal, 2 anodal and one sham session to each subject to improve the strength of the findings. We will have total 75 sessions and 150 data points (pre and post tsDCS outcome assessment) for each outcome measure. This study will provide a strong neurophysiological data for the implementation of future clinical randomized controlled trial studies to evaluate the effects of tsDCS combined with rehabilitation therapy.

8. POTENTIAL RISKS/DISCOMFORTS:

tsDCS: Transcutaneous Spinal Direct Current Stimulation (tsDCS) is a noninvasive procedure in which a device sends a small Direct Current (DC) across the skin to modulate spinal function. The use of tsDCS in therapeutic protocols to date has not resulted in severe adverse effects. In addition our protocol of 2.5mA has been used by other researchers with no significant adverse events

SSEP: Somatosensory evoked potential is recording electrical signals of sensation going from body to brain. Recording electrodes are attached to the scalp and arm. The stimulus will last about 2 minutes at a time and may cause some twitching and tingling sensation in the target area. However it is painless and carries no significant risk.

Spinal reflexes measurement: Stimuli above the action threshold of peripheral nerves will be administered through skin. This might cause some discomfort that is anticipated to be mild and easily tolerated by the subjects. Also skin irritation might occur due to electrode attachment to the skin.

Assessment/Questionnaires: All assessments will be performed in a designated room inside Motor Recovery Laboratory. None of these tests are either painful or uncomfortable to perform. In order to prevent potential embarrassment during the testing the test will be done individually and in private. If subjects feel uncomfortable in answering any of the questions they may stop the study at any time.

9. POTENTIAL BENEFITS:

As with any study focusing on basic research, the subjects will derive no direct benefit. The results of these studies may benefit subsequent future subjects. We envision that in the near future the information obtained from the proposed research will provide a better understanding

for treatment options of SCI population.

10. RISK-BENEFIT RATIO:

The potential improvement of arm and hand movement outweighs the risk of non-invasive spine stimulation, fatigue, pain and discomfort.

11. CONSENT PROCEDURES:

Informed consent will be obtained from the subject at Motor Recovery Laboratory at The Institute for Rehabilitation and Research. After the patient is identified by the PI and her research team study criteria and he/she is interested in participating, informed, written consent will be obtained by a member of the research team.

In addition a photography/videotaping consent will be obtained from the subject, if he/she agrees to be photographed / videotaped during the assessments or treatment sessions.

12. CONFIDENTIALITY PROCEDURE:

All data will be coded with identification number, database will be in a password –protected computer and kept in a locked file cabinet.

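### Section 4 does not say that the 15 random orders are balanced over the five sessions, and Section 7 names no period effect; a balanced list with a period term would avoid an average variance cost of about 7.5%.

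*Combined protocol and SAP*

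**What the plan says.** Section 4 (Description of Study) fixes what each subject receives: "Each subject will receive five tsDCS (2 cathodal, 2 anodal and 1 sham) conditions at T10-T11 spinal level in a random order". The screening paragraph of that section describes sealed, numbered envelopes that hold the order for each subject. On how the orders are produced it says "Sequence will be generated by a random number generator". It mentions no Latin or Williams square, no blocking of orders, and no other constraint on how conditions fall over the five sessions.

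Outcomes are taken before and after stimulation at every session. For the H-reflex outcome, "The difference between pre and post Hmax/Mmax ratio will be measured".

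Section 7 (Data Analysis) gives the model in one sentence: "We will use repeated measures analysis of covariance to estimate the effect" "of group on outcome measures". It names no period, session or sequence term.

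The trial has two stated products. Section 2 says "This pilot study will provide preliminary support and effect sizes that will be used in a larger federally funded study". Section 7 gives the reason for 15 subjects as a literature review "to determine the optimal polarity for future studies".

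**The concern.** A random number generator is a tool, not a scheme. It could draw each subject's order independently, draw 15 different orders, or permute a prepared balanced list, and these designs differ in precision.

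Period is a natural term in a five-period crossover. Once it is fitted, any imbalance of conditions over periods costs precision in every treatment contrast. Sham is the most exposed condition, because each subject has only one sham session. If period is left out, a drift over visits in the response to stimulation enters the contrasts by chance. A shift in the level at a visit is a lesser worry, because the same-day baseline largely removes it.

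The pilot exists to supply effect sizes and to choose a polarity, so precision is what it delivers.

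**Working it through.** **The plan's own figures.** 15 subjects x 5 sessions = 75 sessions, and 75 x 2 = 150 pre and post values per outcome. Both match Section 7. The sample size has no stated alpha, power, effect or SD, so there is no formula to reproduce.

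**How uneven independent orders are.**
- Distinct orders of two anodal (A), two cathodal (C) and one sham (S): 5!/(2! 2! 1!) = 30.
- P(exactly 3 sham in every period) = 15!/(3!^5 x 5^15) = 0.0055.
- P(some period has no sham) = 5(0.8^15) - 10(0.6^15) + 10(0.4^15) - 5(0.2^15) = 0.171.
- In simulation, some period holds 6 or more of the 15 sham sessions in about 30% of lists.

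**Precision without a period term.** Take one pre-post change per session, subject effects, and a residual SD of 1:
- anodal-sham variance = (1/2 + 1)/15 = 0.1000, so SE = 0.316;
- anodal-cathodal variance = (1/2 + 1/2)/15 = 0.0667.

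**Precision with period fitted** (least squares with subject, period and condition effects):

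| How the orders are produced | Anodal-sham variance | Anodal-cathodal variance | Mean rise |
|---|---|---|---|
| Balanced over periods | 0.1000 | 0.0667 | 0% |
| Independent draws (mean of 5,000 lists) | 0.1075 | 0.0717 | 7.5% |
| 15 different orders out of the 30 | about 0.1037 | about 0.069 | about 3.7% |

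A separate run of 20,000 independent lists gave mean rises of 7.5% to 7.6%, a median near 6.1%, and a 5th to 95th percentile range of about 1.2% to 19%. The mean rise in SE was about 3.7%. In subjects, the loss is 15 x (1 - 1/1.076) = 1.1 on average and 15 x (1 - 1/1.19) = 2.4 at the 95th percentile.

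**If period is not fitted.** The documents give no drift, so assume a linear drift of 1 SD in the pre-post change from the first to the fifth visit, or 0.25 SD per visit. Session numbers 1 to 5 have variance 2.5 (divisor n - 1). The anodal mean minus the sham session has squared weights summing to 1/4 + 1/4 + 1 = 1.5. The difference in mean session number over 15 subjects therefore has SD = sqrt(2.5 x 1.5/15) = 0.50. The chance offset in anodal-sham has SD 0.50 x 0.25 = 0.125, with a 95th percentile of about 0.24, against the SE of 0.316. The total variance is 0.1000 + 0.125^2 = 0.1156.

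A drift of 1 SD in level only gives no offset for change scores. With a baseline slope b in the analysis of covariance, the offset SD is (1 - b) x 0.125, which is 0.0625 for b = 0.5 and 0.0125 for b = 0.9 (assumed slopes).

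**Type I error with the 1 SD drift in response** (4,000 simulated trials; simulation error sqrt(0.05 x 0.95/4000) = 0.003):
- independent orders: 0.054 without period, 0.047 with period;
- balanced orders: 0.031 without period, 0.053 with period.

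The 0.031 arises because balance removes the drift from the estimate but not from the residual: the mean reported SE is 0.339 and the actual SD is 0.314. Balance and the period term therefore belong together.

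**The case against.** The strongest reply is that the 7.5% does not arise under the model as written. It needs two things that the protocol does not state: independently drawn orders and a fitted period term. Section 7 does not list the within-subject factors of its repeated measures model, so a session factor is neither planned nor excluded. The generator wording is also compatible with different orders (about 3.7%) or a balanced list (0%).

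Without a period term, harm requires the response itself to drift, and the documents give no reason to expect a large drift. A 0.5 SD drift adds 0.125^2 x 0.25 = 0.0039 to 0.1000, or about 4%. With random orders, fitting period pays only when the drift exceeds sqrt(0.0075/0.0156), about 0.7 SD. Finally, 3.7% on a standard error is unlikely to change the conclusions of an exploratory pilot, and the analysis is valid either way.

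All of this is correct, and it limits the point to a modest gain in efficiency. It does not remove the point. Only one list will be realised, and it may cost 1% or 19%. A balanced list with a period term is protected against both the imbalance and the drift. The choice is nearly free now and cannot be made after the sessions have been given.

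**Conclusion.** The concern holds as a point of efficiency. The protocol states neither balance over sessions nor a period term. If orders are drawn independently and period is fitted, the active-sham and anodal-cathodal contrasts lose about 7.5% in variance on average, and about 19% or more in the worst 5% of lists. If 15 different orders are drawn, the mean loss is about 3.7%; with a balanced list it is zero. If period is not fitted, there is no cost unless the pre-post change drifts, and the drift sizes used above are assumptions. Estimates remain unbiased and the type I error stays near 5% with random orders.

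Exact balance requires all 15 subjects to complete all five sessions, but most of the advantage survives dropout. With 1, 2 or 3 subjects leaving early at a random visit, the anodal-sham variances for independent and balanced lists are 0.1126 and 0.1047, 0.1187 and 0.1098, and 0.1248 and 0.1155. Independent orders still carry about 7% to 8% more variance.

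**What to change.** Before enrolment, fix a list of 15 orders with exactly 3 sham, 6 anodal and 6 cathodal sessions in each period, and use the random number generator to permute that list into the numbered envelopes. One list that meets this is:

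SCACA, SAACC, SCAAC, ASACC, CSAAC, ASCCA, CASCA, CASAC, CCSAA, CACSA, ACCSA, AACSC, CACAS, ACACS, ACCAS.

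In it, sham is preceded 6 times by anodal and 6 times by cathodal, and comes first 3 times. Fitting period with this list leaves the contrast variances unchanged. The list should be kept from the blinded evaluator.

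In Section 7, add period (1 to 5) as a fixed effect. If balance is already intended, say so in the randomization paragraph of Section 4; the period term is still needed.

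The cost is one script, one sentence and 4 degrees of freedom. Residual degrees of freedom go from 75 - 15 - 2 = 58 to 54, and the critical t from 2.002 to 2.005, so confidence intervals are about 0.16% wider. No subject or visit is added.

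### Does the H-reflex procedure cancel the pre-post change in Hmax/Mmax, or leave Hypothesis 1 untested because no stimulation rate is given?

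*Combined protocol and SAP*

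**What the plan says.** Section 4, under the Hmax/Mmax heading, states the outcome as a commitment: "Immediately before and after application of tsDCS we will measure Hmax/Mmax ratio obtained from soleus muscle by stimulation of tibial nerve". The analysed quantity follows: "The difference between pre and post Hmax/Mmax ratio will be measured". The same paragraph gives the meaning and purpose of the ratio: "changes in the ratio of maximal H-reflex amplitude and maximal M-wave amplitude (Hmax/Mmax) provide a rough estimate of modulation in spinal excitability".

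It then turns to normalization: "It is necessary to normalize this value so between-subject comparisons can be made". After a sentence on sources of amplitude variation, it continues: "The most advocated method of H-reflex normalization is eliciting the H-reflex at a percentage of the Mmax". The method is explained as finding Mmax and then "adjusting the stimulation intensity to produce an H-reflex with amplitude equal to some percentage of the Mmax amplitude", with a literature citation.

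For the recordings after stimulation, Section 4 (Post tsDCS) says: "Similar procedures will be followed as pre intervention assessments for Hmax/Mmax ratio, SSEP and vital signs recordings".

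On rate, Section 2 expects a change in the H-reflex pathway "when tested using stimulation rates at which post-activation depression is present". Hypothesis 1 and the central hypothesis in Section 3 refer to a change in Hmax/Mmax and carry no rate condition. The only nerve-stimulation rate in the document, 3–5 Hz, belongs to the SSEP paragraph.

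**The concern.** Two different measurements sit in one paragraph. Hmax is the peak of the reflex across stimulus intensities. An H-reflex tuned to a chosen percentage of Mmax is a point picked by the operator. The text calls normalization necessary and then describes only the second measurement. An evaluator who took that as the instruction, and repeated it after tsDCS because the post procedure is to be similar, would set the reflex to the same percentage twice. The change score would then hold only tuning error, and a real effect of stimulation would show as a shift in the required intensity, which is not an outcome of this study.

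The missing rate raises a second doubt. If the expected effect appears only at rates that produce post-activation depression, recordings at a rate without it would not test the Section 2 version of the hypothesis. Section 2 also says that the pilot's effect sizes will feed a larger study, so an attenuated measure would carry forward.

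**Working it through.** **No planned figure is at issue.** Section 7 bases the 15 subjects on a literature review and gives no effect size, SD, alpha or power. Its counts are consistent: 15 × 5 = 75 sessions, and 75 × 2 = 150 data points per outcome.

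**When does the change score vanish?** The inputs here are assumed, since the documents give no recruitment curve. Let H/Mmax at intensity I be g × 0.5 × Φ((I − 50)/8), where g is reflex gain. Before tsDCS g = 1; after it g = 0.8 or 1.2, a true change of 20% either way. Let p be the target fraction of Mmax (0.10, 0.20 or 0.30). There are three ways to record:

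- **(a) Hmax/Mmax at each time point.** Difference = 0.5g − 0.5 = 0.5(g − 1), which is −0.10 or +0.10.
- **(b) Intensity set at baseline to give p, then held.** Difference = gp − p = p(g − 1), which is ±0.02, ±0.04 and ±0.06 for the three targets.
- **(c) Intensity re-tuned to p after tsDCS.** Difference = p − p = 0. The effect moves into the intensity required: shifts of 1.34, 2.03 and 3.37 units for g = 0.8, and −1.01, −1.42 and −2.03 for g = 1.2.

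The results for (b) and (c) do not depend on the curve's shape, only on the gain being multiplicative. The change score is lost under (c) alone.

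**Which reading does the text support?** The sentences that commit the study name Hmax/Mmax and its pre-post difference, which is (a). The Figure 1 caption, the Post tsDCS paragraph, Table 1 and Hypothesis 1 name the same measure. The percentage text describes the method generally, leaves the percentage open and does not say the study will apply it. Its stated purpose is comparison between subjects, whereas the outcome is a difference within a subject and session. The value to be normalized can also be read as raw H amplitude, in which case dividing by Mmax is already the normalization. Reading (c) needs two further steps that appear nowhere: that a tuned H replaces Hmax, and that the stimulus is reset to the same target afterwards.

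**Rate.** Section 2 states the condition and Section 4 gives no value. No unsuitable rate is specified, so nothing in the procedure contradicts Section 2. The loss from a poor choice of rate cannot be sized from the documents.

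**The case for a change.** The strongest case for a change is that the percentage method is the only technique described for obtaining H amplitude. No recruitment curve is mentioned, and nothing says whether intensity is held or reset after tsDCS. Readings (a) and (b) both keep a signal but on different scales (0.10 against 0.02 to 0.06 in the example), which matters for a pilot meant to supply effect sizes. Inconsistent recording could not be repaired in the analysis, and a few sentences would settle it. The rate is absent although Section 2 depends on it, and the title of the prior tsDCS study cited there as altering the H-reflex concerns post-activation depression.

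Much of this stands as description. The paragraph does not connect the percentage method to the outcome, and the rate is not written down. It does not stand that the protocol prescribes the tuning or forces the difference to zero, because both depend on the unstated re-tuning. Nor does it follow that the study must either lose its signal or measure something else. The most direct reading, Hmax and Mmax recorded before and after at a rate that respects Section 2, does neither. The uncertainty over scale also shrinks once the outcome is taken as named, because only (a) is Hmax/Mmax.

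**Conclusion.** No change to the plan follows. Carried out as written, with Hmax over Mmax recorded at each time point, the outcome can show an effect of stimulation; in the example a 20% gain change appears in full, as 0.10. The zero result belongs to one reading that the protocol neither states nor excludes and that conflicts with its own definition of the outcome. What remains is acquisition detail: how intensity is handled around tsDCS, and one H-reflex rate. A laboratory experienced with this reflex would fix both in its working procedure before the first session.

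This rests on two assumptions: that the evaluators measure the named ratio, and that the rate is one at which post-activation depression is present and is the same before and after tsDCS in all five sessions. The sizes in the example come from an assumed curve and show only which readings keep a signal; they do not predict this trial's results.
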